- 1. To assess the safety and efficacy of the current FDA-approved 1 mg b.i.d. varenicline for smoking cessation in comparison with placebo when used in a simulated OTC study with no behavioral support provided.
- 2. To assess the safety and efficacy of .5mg b.i.d. varenicline in comparison with 1mg b.i.d. varenicline and placebo when used in a simulated OTC study with no behavioral support provided.

Secondary Objectives

- 1. To evaluate whether subject specific characteristics (e.g. socioeconomic status, ethnicity, smoking history, etc.) moderate primary (safety and efficacy) and secondary (adherence) outcomes.
- 2. To evaluate medication use patterns to assess whether varenicline is being used as indicated on the label, and to determine if medication adherence mediates cessation outcomes between-subjects.

3. In a subsample of participants, to examine how medication adherence, withdrawal, and side effects (e.g. nausea and sleep disturbance) vary within-subjects and are associated with smoking status using EMA in the first two critical weeks of medication use.

[figure not shown]
Hypotheses

- 1. Quit rates in the 1 mg b.i.d. varenicline condition will be significantly higher than the placebo medication condition when provided as an OTC medication.
- 2. Quit rates in the .5 mg b.i.d. varenicline condition will be comparable to the 1mg b.i.d. varenicline condition, and will be significantly higher than the placebo medication condition, when provided as an OTC medication.
- 3. Side effects will show a dose response relationship, with effects lowest in the placebo group.

C. EXPERIMENTAL METHODS Study Design

The primary objective of this study is to assess the efficacy of two different doses of varenicline used in a simulated OTC intervention relative to placebo (total N = 432). The design is a three-group placebo-controlled, double blind, block randomized clinical trial (as indicated in the figure), where participants will be randomly assigned to one of three

conditions: (1) 1 mg b.i.d. varenicline for 12 weeks, which is the current FDA-approved dose, (2) 0.5 mg b.i.d. varenicline for 12 weeks, or (3) placebo.

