- Adverse Events
- Concomitant Medications
- Smoking Status and Resource Utilization Assessment (See Appendix 9) (Brief site administered questionnaires assessing smoking status, smoking cessation resources used since last study visit
- Medication Adherence, and Perceived Efficacy Assessment (see Appendix 10) (Brief site administered questionnaires assessing pills taken since last study visit, and perceived efficacy of the medication.
- Modified Cigarette Evaluation Questionnaire (mCEQ), see Appendix 11). This 15item staff or subject administered questionnaire assesses the degree to which smokers experience the reinforcing effects of smoking.

Weeks 4, 8 for the In-person Cohort

- Breath Carbon Monoxide test
- Minnesota Nicotine Withdrawal Scale
- Adverse Events
- Concomitant Medications
- Smoking Status, and Resource Utilization Assessment
- Medication adherence and Perceived Efficacy Assessment
- Assess medication use by retrieving unused medication
- Modified Cigarette Evaluation Questionnaire (mCEQ)
- Dispense additional Investigational Product

*All questionnaires at this visit will take place, as much as possible, on the phone prior to the subject attending the visit as to minimize contact in response to the COVID-19 pandemic

Week 12 for the In-person Cohort

- Body weight
- Breath Carbon Monoxide test
- Minnesota Nicotine Withdrawal Scale
- Adverse Events
- Concomitant Medications
- Smoking Status, and Resource Utilization Assessment

- Medication Adherence and Perceived Efficacy Assessment
- Assess medication use by retrieving unused medication
- Modified Cigarette Evaluation Questionnaire (mCEQ)

*All questionnaires at this visit will take place, as much as possible on the phone prior to the subject attending the visit as to minimize contact in response to the COVID-19 pandemic

Week 13 (telephone call) for the In-person Cohort

- Smoking Status, and Resource Utilization Assessment
- Adverse Events
- Minnesota Nicotine Withdrawal Scale
- Concomitant Medications including Chantix[™] or other smoking cessation aids

Week 26 for the In-person Cohort

- Telephone call
- Smoking Status and Resource Utilization Assessment
- Body weight
- Breath Carbon Monoxide test

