Alternatives to Participation. Any of those who are not eligible for the study will be referred to the free smoking cessation quitline available in both states. In addition, any participants who elect to drop out of the study will also be referred to the state quitline, or could potentially obtain Chantix or another medication from their healthcare provider.

Investigational Product

Product: Varenicline (generic name, product name is Chantix™)

Doses: 0.0 mg, .5mg and 1.0 mg

Product Form: Pill

Product Administration: Oral, with water

Manufacturer: Pfizer

Varenicline and Placebo. In this study, participants will be randomly assigned in double-blind fashion to use one of two doses of varenicline (.5 mg b.i.d. or 1.0mg b.i.d.) or placebo (see study design above). Both varenicline and the placebo will look identical and be in identical packaging.

Medication Dosing. Participants assigned to the 1.0 mg b.i.d. condition, which is the current FDA-recommended dosing, will follow the recommended varenicline titrated dosing schedule as follows: days 1 through 3: 0.5mg, one daily; days 4 through 7: 0.5mg, twice daily; days 8 through end of treatment: 1mg, twice daily. Those assigned to the 0.5mg bid. condition will begin use 0.5mg once daily days 1 through 3, then will begin using 0.5 b.i.d on day 4 through the end of the study. Those assigned to the placebo condition will use pills that look identical to those that are being used in the other conditions but contain no medication. The subjects in the placebo group will also titrate during the first 7 days (1 pill days 1-3, 2 pills for the duration of the treatment period). All participants will take identical looking pills at the same time throughout the study, with the only difference being the amount of varenicline included in each pill.

Product Packaging. Medication packaging for this study will be implemented at the ASU site. Two study staff will work together to package the medications, and all packaging will be double checked and tracking forms maintained by the staff to assure quality control. Medications will be shipped by FedEx or equivalent to LACT (or directly to participants if they are participating in the study remotely), where study product will be checked and a report provided back to ASU within 24 hours indicating whether all sent medications were received.

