Product will be packaged for each in-person cohort study visit as follows: (1) Baseline to Week 4: During the first week after baseline, when participants start and ramp up their dose, standard multi-compartment pill organizer containers will be provided to study participants with their assigned dosing regimen (as indicated above). In addition, participants will be provided 28 days of their maintenance twice daily dose in a standard child resistant-pill bottle. This will allow for an extra 7 days of IP to account for delays in attending the Week 4 visit. (2) Week 4 and Week 8: Medication will be provided in a pill

bottle at each visit, and in order to assure adequate supply in case of a delay in study visits, each container will contain enough product to last 5 weeks. All containers will be child-resistant for added protection, and labeled appropriately for the study.

Product will be packaged **for the remote cohort** as follows: product will be mailed after the second baseline visit. The first week of starting the medication, when participants start and ramp up their dose, standard 7-day multi-compartment pill organizer containers will be provided to study participants with their assigned dosing regimen (as indicated above). In addition, participants will be provided 12 weeks of their maintenance twice daily dose in a standard child resistant-pill bottle. All containers will be child-resistant for added protection, and labeled appropriately for the study.

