2	Did cigarettes taste good?
3	_Did you enjoy the sensations in your throat and chest?
4	_Did smoking calm you down?
5	_Did smoking make you feel more awake?
6	_Did smoking make you feel less irritable?
7	Did smoking help you concentrate?
8	_Did smoking reduce your hunger for food?
9	_Did smoking make you dizzy?
10	_Did smoking make you nauseous?
11	_Did smoking immediately relieve your craving for a cigarette?
12	_Did you enjoy smoking?

Smoking Status and Resource Utilization

Smoking status

At al	l visits

- 1. Did you smoke any cigarettes, even a puff, since your last visit? Yes No
- 2. [If Yes to 1] Did you smoke any cigarettes, even a puff, in the last 7 days?

It has been approximately	weeks since your last visit.
3. On approximately how many days	s did you smoke?
4. On the days that you smoked, wh	at is the average number of cigarettes that you
smoked?	

Resource utilization

At all visits

- a. Since your last visit, which of the following additional things have you tried to reduce or quit smoking? Check all that apply.
- a) A pamphlet or book
- b) Individual or group counseling
- c) Telephone counseling / quitline
- d) Nicotine patch, gum, nasal spray, lozenge, or inhaler
- e) E-cigarettes
- f) Zyban / bupropion
- g) Switching to chewing tobacco or snuff
- h) Switching brands
- i) Cutting back
- j) An Internet quit smoking program
 k) Alternative methods like herbs, lasers, homeopathic medicines, prayer, acupuncture, or hypnosis

 Somet 	hing else:	
---------------------------	------------	--

Medication compliance and perceived efficacy

Medication	efficacy	and com	npliance

Λt	വ	\ / /	101	t-c
Αt	aı	ı v	ı	ເວ

- 5. This medication is helping me/has helped me quit smoking.
- a) Strongly disagree
- b) Somewhat disagree
- c) Neither agree nor disagree

d) Somewhat agree e) Strongly agree f) Don't know
At Week 2 telephone call only a. It has beendays since your last visit. After the first 3 days of taking the study medication the instructions were to take 2 pills per day. Approximately what percentage of days did you take: itwo doses per day iione dose per day iiino doses
At the Week 4, 8 and 12 visits 6. It has been number of days since your last visit.
Approximately what percentage of days did you take:two doses per dayone dose per dayno doses
Ask #7 only if any study product was reported as not used as recommended 7. Main reason for not using medication as recommended (check only one): forgotside effectnot workingdon't needother Specify:

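### The main-study dosing form has no category above two doses a day and no clear item on days 1–3, which limits the assessment of label-concordant use

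*Combined protocol and SAP*

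**What the plan says.** Secondary Objective 2 (Specific Aims) reads: "To evaluate medication use patterns to assess whether varenicline is being used as indicated on the label". Under Behavioral Support, staff give no usage instruction after randomization beyond the consent form and the handout, so correct use is something the trial observes and does not coach.

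Medication Dosing gives the pill schedule. For placebo it is "1 pill days 1-3, 2 pills for the duration of the treatment period", and the arms take look-alike pills on a common timetable. In the 1 mg arm, strength also changes within the first week: "days 4 through 7: 0.5mg, twice daily; days 8 through end of treatment: 1mg, twice daily".

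Appendix 10 collects use by self-report. The Week 2 item says "After the first 3 days of taking the study medication the instructions were to take 2 pills per day" and then asks for percentages of days with two, one or no doses. At Weeks 4, 8 and 12 the item is "Approximately what percentage of days did you take:two doses per dayone dose per dayno doses". Item 7, "Main reason for not using medication as recommended (check only one", is put only to those who reported use other than as recommended. It lists four reasons and an open 'other' field.

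There are two further sources:
- **Returned medication.** In-person visits at Weeks 4, 8 and 12 include "Assess medication use by retrieving unused medication". Remote participants mail theirs back once, at Week 12. The Statistical Analysis Plan allows adherence to be analysed as a pill count.
- **EMA sub-study.** An evening diary asks for the number of pills each day during the first two weeks.

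On supply, remote participants receive a first-week organizer, and in addition "participants will be provided 12 weeks of their maintenance twice daily dose in a standard child resistant-pill bottle".

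**The concern.** A trial of unsupervised use has to be able to see departures from the label in both directions. The form describes under-use in steps but has no place for a day above two pills, and such a day would most naturally be entered in the category that represents full adherence. Nothing in that answer would then trigger item 7.

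The first week is also thinly covered. No item asks separately about days 1–3, and none asks whether the organizer was used before the bottle. In the 1 mg arm the two containers hold different strengths of look-alike pills.

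At stake is the part of Secondary Objective 2 that concerns label-concordant use. As built, the form mainly measures under-use. The primary abstinence endpoint does not depend on it.

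**Working it through.** **1. Inputs.** One pill a day on days 1–3, then two a day (Medication Dosing). Organizer plus 28 days in a bottle at baseline, and 5-week containers at Weeks 4 and 8, for the in-person cohort; organizer plus 12 weeks for the remote cohort (Product Packaging). EMA N = 75; planned N = 432.

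**2. The plan's own figure.** Organizer week: 3×1 + 4×2 = 11 pills. First in-person supply: 11 + 28×2 = 67. Needed to day 28: 11 + 21×2 = 53. Surplus: 67 − 53 = 14 pills = 7 days, as the protocol states.

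**3. Room for over-use.** Needed for 84 days: 3×1 + 81×2 = 165 pills.
- Remote: 11 + 84×2 = 179, surplus 14.
- In-person: 67 + 70 + 70 = 207, surplus 42 before returns.

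**4. What the form and the count would show in the two-pill period**, assuming days above two are entered as two doses:

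| Pattern | Mean pills per day | Net count against schedule | Form |
|---|---|---|---|
| Two every day | 2.0 | 100% | 100% two |
| Three on 20% of days, two otherwise | 0.20×3 + 0.80×2 = 2.2 | 110% | 100% two |
| Four on 50% of days, none otherwise | 0.50×4 = 2.0 | 100% | 50% two, 50% none |

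The form cannot separate the second pattern from perfect use, but the count can. For a remote participant the excess is 0.20×81 = 16.2 pills (16.8 if spread over all 84 days), more than the surplus of 14, so nothing would be left to return. The third pattern passes the count and looks like missed doses on the form.

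**5. Week 2 item, 14 days on medication.**
- Correct titration, all days counted: 3/14 = 21.4% one-dose days and 11/14 = 78.6% two-dose days.
- Correct titration, days 4–14 only: 100% two-dose days.
- Two pills from day 1: 100% two-dose days on either base.

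If only days 4–14 count, the error and correct use are identical. If all days count they differ, but the participant who titrated correctly shows the lower two-dose percentage. The form does not say which base applies.

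**6. Can the count find the day 1–3 error?** It adds 3 pills to 53 by day 28, or 3/53 = 5.7%, and three missed pills cancel it.

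**7. EMA coverage.** 75/432 = 17.4% of the planned sample, for two weeks. EMA steps and the EMA willingness criterion appear in the in-person lists but not in the remote lists, so remote cover may be nil.

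**The case against.** The strongest reply is that the form is not the only source. Returned medication is counted, pill count is a named adherence variable, and the EMA diary spans the titration period. That stands. A reader might infer that over-use cannot be recorded anywhere in the trial, and the documents do not support this: a steady excess such as three pills on 20% of days would show in the count. What remains is that a count gives a net total with no day-level pattern, remote participants supply it once, and the Statistical Analysis Plan gives no expected count or definition of over-use.

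Four other strong readings also go too far.
- **The Week 2 item leaves out days 1–3.** It opens by asking for the days since the previous visit, so all days may be meant. The fault is an undefined base.
- **The listed reasons cover only under-use.** The 'other' field is open, and a belief that the drug is not working could also explain extra pills. The limitation is that full adherence on the dosing item does not lead to item 7.
- **An adverse event caused by over-use could not be linked to it.** Events are asked about at each visit and a licensed medical professional judges causality. Nothing shows that dosing is left out of that judgement.
- **Each Week 4 and Week 8 container holds 14 spare pills.** This needs 28-day intervals. The target days in Table 2 (28, 52 and 98) give 24 and 46 days.

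It is also fair to say that asking about container order could cue correct use in a study that withholds usage instruction, and that such order changes strength only in the 1 mg arm.

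**Conclusion.** The point holds as a limitation of the main-study self-report form. It has no valid entry for a day above two pills and no clear item on days 1–3. Elsewhere, over-use is visible only as a net count. Early titration errors can be picked out only within the EMA subset of 75, since the Week 2 percentage is ambiguous and a 3-pill excess is easily cancelled.

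The conclusion rests on three assumptions. Days above two pills would be entered as two doses; this is the natural choice, but no coding rule says so. The form ends at item 7, which is as far as it appears in the text available to this review. The EMA diary can record counts above one; only the options 0 and 1 are visible in that text, possibly through conversion loss. The documents give no basis for estimating how often over-use or cancelling patterns would occur, so the effect on Secondary Objective 2 cannot be quantified further. This is a measurement gap in a secondary objective, worth closing because the remedy is small. No dosing rule is at issue.

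**What to change.** In Appendix 10:
- Add a category for more than two doses a day, with the largest number taken in one day.
- At Week 2, define the percentage over day 4 onward and ask separately, in neutral wording, how many pills were taken on each of days 1, 2 and 3.
- If the order of organizer and bottle is asked, word it neutrally and ask it only after the first week is over.

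In the Statistical Analysis Plan, under Secondary Objective 2, report over-use and titration deviations by arm, separately from under-use and beside the net pill count.

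The cost is under a minute per contact and one descriptive table, with no new visit. The drawbacks are two form versions within the adherence variable and missing values for participants already past Week 2. Both should be stated when the results are reported.

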 peeling skin, or blisters in your mouth.
- Use caution when driving or operating machinery until you know how the study medication affects you. Decrease
 the amount of alcohol you drink while taking the study medication until you know if the study medication affects your
 ability to tolerate alcohol. Some people have experienced the following when drinking alcohol during treatment with
 CHANTIX:
- increased drunkenness (intoxication)
- unusual or sometimes aggressive behavior
- no memory of things that have happened

For additional information, contact study staff and review the consent form.

SMOKING CESSATION HELP: If you would like support to help you quit smoking, you can get free help by calling the smoking cessation quitline for your state: [name]

Revised: 1/22/18 for research purposes

EMA Items for Scheduled Prompts

Items for first scheduled prompt of the day

- 1. How good did you sleep last night?
 - a. Very bad
 - b. Bad
 - c. Ok
 - d. Good
 - e. Very good
- 2. Did you have any unusually vivid, realistic, or crazy dreams last night?
 - a. Yes
 - b. No
- 3. How nauseous do you feel right now?
 - a. Not at all
 - b. A little
 - c. Somewhat
 - d. A lot
 - e. Extremely
- 4. How is your mood right now?
 - a. Very bad
 - b. Bad
 - c. Ok
 - d. Good
 - e. Very good
- 5. How much do you want to smoke a cigarette right now?
 - a. Not at all
 - b. A little
 - c. Somewhat
 - d. A lot
 - e. Very, very much

Items for the remaining scheduled prompts of the day

- 1. How nauseous do you feel right now?
 - a. Not at all
 - b. A little
 - c. Somewhat
 - d. A lot
 - e. Extremely
- 2. How is your mood right now?
 - a. Very bad
 - b. Bad

- c. Ok
- d. Good
- e. Very good
- 3. How much do you want to smoke a cigarette right now?
 - a. Not at all
 - b. A little
 - c. Somewhat
 - d. A lot
 - e. Very, very much

EMA Items for Evening Daily Diaries

- 1. How many cigarettes did you smoke today?
 - a. [Drop down menu, 0-60+]
- 2. How many study pills did you take today?
 - a. 0
 - b. 1
- 3. Any other thoughts or feelings that you want to tell us about?
 - a. [open response]

MEDICATION GUIDE CHANTIX® (CHANT-iks)

(varenicline) Tablets

What is the most important information I should know about CHANTIX?

When you try to quit smoking, with or without CHANTIX, you may have symptoms that may be due to nicotine withdrawal, including:

- · urge to smoke
- depressed mood
- trouble sleeping
- irritability

- frustration
- anger
